In a Phase 1 study that assessed the safety and tolerability of itacitinib in combination with corticosteroids, 30 aGVHD subjects were randomized to 1 of 2 treatment cohorts (200 mg cohort, n = 14; 300 mg cohort, n = 16). One subject was randomized to the 300 mg cohort but withdrew from the study before starting treatment. One DLT of Grade 3 thrombocytopenia was reported in 1 subject with pre-existing thrombocytopenia who was randomized to the 300 mg cohort. Adverse events reported in greater than 20% of all subjects include diarrhea, hypokalemia, peripheral edema, hyperglycemia, abdominal pain, hypophosphatemia, fatigue, headache, hypomagnesemia, and sepsis. Thrombocytopenia and platelet count decreases were observed in 24.2% and 20.7% of subjects, respectively, with a higher proportion of these events occurring in the 300 mg cohort, although a higher incidence of pre-existing thrombocytopenia was also observed in this group. The Day 28 ORR in first-line aGVHD subjects in both treatment cohorts was 83.3%; for subjects with SR-aGVHD, the overall Day 28 ORR was 64.7% (200 mg cohort, 62.5%; 300 mg cohort, 66.7%). Most responses occurred within the first 14 days of treatment, and responses were durable, with a median DOR of 130 days and 136 days in the 200 mg cohort and 300 mg cohort, respectively. Complete response rates of 66.7% and 17.6% were reported for first-line and SR-aGVHD cohorts, respectively. Pharmacokinetics of itacitinib were evaluated using plasma samples collected predose and at 1 hour, 2 hours, and 4 to 8 hours postdose on Study Days 1 and 7. Although intersubject variability was found to be high, PK exposure ( $C_{max}$  and AUC) was consistent with historical data, and a large overlap in steady-state exposure was observed between the 200 mg and 300 mg cohorts. The higher incidence of thrombocytopenia and DLT of thrombocytopenia in the 300 mg cohort, as well as similarities in PK and efficacy between dose groups, led to the identification of the 200 mg dose of itacitinib as the recommended phase 2 dose for future GVHD studies (Schroeder et al 2016). The treatment compliance rate and median duration of treatment were also higher in the 200 mg

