2.2. Study Objectives and Endpoints

[Table 1](#) presents the study objectives and endpoints.

Table 1: Objectives and Endpoints

Primary Objective	Primary Endpoint
Compare the efficacy of itacitinib in combination with corticosteroids versus placebo in combination with corticosteroids in terms of ORR at Day 28 in subjects with aGVHD.	ORR at Day 28, defined as the proportion of subjects demonstrating a CR, VGPR, or PR.
Key Secondary Objective	Key Secondary Endpoint
Compare the efficacy between treatment cohorts at a subsequent key clinical landmark.	NRM at Month 6, defined as the proportion of subjects who died due to causes other than malignancy relapse at Month 6.
Secondary Objectives	Secondary Endpoints
Compare additional response and longer-term efficacy outcomes between treatment cohorts.	ORR, defined as the proportion of subjects demonstrating a CR, VGPR, or PR at Days 14, 56, and 100.
	NRM at Months 9, 12, and 24.
	DOR for responders will be calculated. The DOR is defined from the time of the onset of response to loss of response. Subjects who died or discontinued will be censored at the death date or the previous assessment.
	TTR, defined as the interval from treatment initiation to first response.
	Relapse rate of malignant and nonmalignant hematologic diseases, defined as the proportion of subjects whose underlying hematologic disease relapses.
	Malignancy relapse-related mortality rate, defined as the proportion of subjects whose malignancy relapses and has a fatal outcome.
	FFS, defined as the proportion of subjects who are still alive, have not relapsed, have not required additional therapy for aGVHD, and have not demonstrated signs or symptoms of cGVHD, at Month 6.
OS, defined as the interval from study enrollment to death due to any cause.	
Assess the incidence and severity of AEs and SAEs.	Clinical safety data (eg, AEs, infections) will be tabulated and listed.
Evaluate the PK of itacitinib when administered in combination with corticosteroids.	C_{max} , C_{min} , t_{max} , AUC, and CL/F.
Evaluate the incidence of secondary graft failure.	Incidence rate of secondary graft failure, defined as > 95% recipient cells any time after engraftment with no signs of relapse, OR retransplantation because of secondary neutropenia ($< 0.5 \times 10^9/L$) and/or thrombocytopenia ($< 20 \times 10^9/L$) within 2 months of transplant.

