7.3.2. Duration of Response for Day 28 Responders

The DOR is defined from the time of the first response to the loss of response (ie, either disease progression or death). Responders who did not progress or die after onset of response will be censored, and response will be ended at either study withdrawal, initiation of new anti-GVHD therapy, or last response assessment before or on the cut-off date, whichever is earliest.

Duration of response will be calculated for every responder as well as Day 28 responders.

The DOR for the Day 28 responders will be assessed using the KM method only for subjects who achieve Day 28 response. The KM curves; medians; 1-, 2-, 6-, 12-, 18- and 24-month (equivalently at Days 30, 60, 180, 365, 547, and 730) survival estimates and 95% CIs will be estimated ([Brookmeyer and Crowley 1982](#)). The DOR will be assessed for each treatment group and also by stratum and Day 28 response status.

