7.3.3. Alternative Ways of Calculating Duration of Response for Day 28 Responders

There are 2 other ways of calculating DOR for Day 28 responders:

- **DOR alternate approach 1** – DOR is defined as the interval from Day 28 to either death or initiation of new anti-GVHD therapy, including a higher corticosteroid dose than that administered at Day 1, whichever is earlier.
- **DOR alternate approach 2** – DOR is defined as the interval from Day 28 to the earliest of death, worsening from best response at or after Day 28 in any organ stage, or initiation of new anti-GVHD therapy (including a higher corticosteroid dose than that administered at Day 1).

Summary statistics and KM estimate will be provided by treatment group. Kaplan-Meier plots will also be provided.

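### The Kaplan-Meier analysis of response duration in Day 28 responders is timed from first response, so up to about three weeks are largely event-free by selection and early durability reads too high

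*SAP*

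**What the plan says.** SAP 7.3.2 sets the time origin and the event: "The DOR is defined from the time of the first response to the loss of response (ie, either disease progression or death"). Study withdrawal, new anti-GVHD therapy and last response assessment are censoring points. On who is covered, it says "Duration of response will be calculated for every responder as well as Day 28 responders", and then "The DOR for the Day 28 responders will be assessed using the KM method only for subjects who achieve Day 28 response". The output follows: curves, medians and estimates at 1, 2, 6, 12, 18 and 24 months. The paragraph closes with "The DOR will be assessed for each treatment group and also by stratum and Day 28 response status".

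SAP 7.3.1.1 classes death, study withdrawal or new anti-GVHD therapy before the Day 28 visit as non-response.

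SAP 7.3.3 adds two alternatives for Day 28 responders with a Day 28 origin. The first reads "DOR is defined as the interval from Day 28 to either death or initiation of new anti-GVHD therapy". The second adds worsening in any organ stage. Both come with Kaplan-Meier estimates and plots.

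The endpoint in SAP Table 1 has no Day 28 condition: "The DOR is defined from the time of the onset of response to loss of response". SAP 7.1 has DOR calculated for every subject with a response. Protocol 9.4.2 plans Kaplan-Meier and a log-rank test for DOR from first response, also without a Day 28 condition.

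**The concern.** Entry to the analysis depends on a status observed at Day 28, while the clock starts earlier. This is immortal time. Someone who responds on Day 7 and dies on Day 20 has a DOR event under SAP 7.3.2, but is a Day 28 non-responder under SAP 7.3.1.1. The event that the analysis should count removes the subject from it. Progression without recovery by Day 28 does the same. New therapy before Day 28 also removes the subject, although SAP 7.3.2 would otherwise only censor there.

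Two things are at stake. The early part of the curve, above all the 1- and 2-month estimates, would look better than the durability of responses from their onset. And the amount of guaranteed time depends on how early a subject responds, so an arm that responds sooner can look more durable with the same rate of loss.

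**Working it through.** The documents give no expected value for DOR, so there is no planned figure to reproduce. The size can only be illustrated.

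**Inputs**
- Grading is weekly for the first 8 weeks (Protocol 7.6.1), so first response falls at about Day s = 7, 14, 21 or 28. The guaranteed gap is g = 28 - s = 21, 14, 7 or 0 days, subject to the 3-day visit windows.
- On Phase 1 timing, Protocol 1.4.2 says "Most responses occurred within the first 14 days of treatment". Two assumed distributions over Days 7/14/21/28 are used: A = 45/35/12/8% (80% by Day 14) and B = 25/35/25/15% (60% by Day 14).
- Median DOR M: 130 days (Phase 1, 200 mg) and the updated 166 days (200 mg) and 189.5 days (300 mg), all from Protocol 1.4.2. These pool first-line and steroid-refractory subjects.
- Exponential loss, independent of the day of first response, is an assumption: S(t) = exp(-λt), λ = ln 2 / M.

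**Formula, no regained responses.** A responder is kept if DOR exceeds g. The fraction kept is K = Σ p(s)·S(28 - s). For any t of 21 days or more, the expected Kaplan-Meier value in those kept is S(t)/K. The curve is scaled up by 1/K, and the median becomes M + (-ln K)/λ.

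**M = 130.** λ = 0.005332; S(21) = 0.8941, S(14) = 0.9281, S(7) = 0.9634.
- A: K = 0.45×0.8941 + 0.35×0.9281 + 0.12×0.9634 + 0.08 = 0.9228, so 7.7% are excluded.
- B: K = 0.25×0.8941 + 0.35×0.9281 + 0.25×0.9634 + 0.15 = 0.9392, so 6.1% are excluded.

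| | All responders | Day 28 responders, A | Day 28 responders, B |
|---|---|---|---|
| 30 days | 85.2% | 85.2/0.9228 = 92.4% | 85.2/0.9392 = 90.7% |
| 60 days | 72.6% | 78.7% | 77.3% |
| 180 days | 38.3% | 41.5% | 40.8% |
| Median (days) | 130 | 145 | 142 |

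**Longer medians, 30 days.** M = 166: 88.2% in all responders, against 94.0% (A) and 92.7% (B), an excess of 5.7 and 4.5 points. M = 189.5: 89.6% against 94.7% and 93.6%, an excess of 5.1 and 4.0 points.

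**Half of the early losses regained by Day 28, first loss counted as the event (assumption).** The denominator becomes 1 - (1 - K)/2. At M = 130 this gives 85.2/0.9614 = 88.6% (A) and 85.2/0.9696 = 87.9% (B), an excess of 3.4 and 2.7 points.

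**Same loss rate, different speed of response.** At M = 130, let one arm respond as 60/30/7/3% (K = 0.9123) and the other as B. The 30-day estimates are 85.2/0.9123 = 93.4% and 90.7%, a gap of 2.7 points with no difference in durability. This contrast is hypothetical.

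**Day 28 origin.** For those kept, the chance of a further 30 days is S(g + 30)/S(g) = S(30) = 85.2%. The built-in survival is gone.

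**The case against.** A reader might infer that DOR as a whole is confined to Day 28 responders. The documents do not support that. The restriction applies to one named analysis. SAP 7.1 and 7.3.2 have DOR calculated for every responder, a split by Day 28 response status may imply responders outside the Day 28 group, Protocol 9.4.2 has no such restriction, and SAP 10.1 declares no change to it. Nothing labels the Day 28 analysis as the main one. What remains is that the SAP spells out Kaplan-Meier output only for Day 28 responders. Part of the list of planned tables is missing from the public copy, so an all-responder table cannot be ruled out.

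A reader might also infer that every response lost before Day 28 is dropped. That is too strong. Steroid re-escalation up to the starting dose is not treatment failure (Protocol 5.2.3), and only a dose above that of Day 1 counts as new therapy (SAP 7.1). A subject who loses response and regains it by Day 28 without new therapy stays in. This reduces the bias but does not remove it, since a death cannot be regained.

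SAP 7.3.3 already starts at Day 28. However, its events are death, new therapy and organ-stage worsening, not the progression or death of SAP 7.3.2. It shows that the right origin is at hand, but it does not correct the SAP 7.3.2 estimate.

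Finally, the curve is labelled as Day 28 responders and misleads only if read as durability from onset. That is fair, but timing it from first response invites exactly that reading.

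**Conclusion.** The defect is real and limited to the Day 28 responder analysis in SAP 7.3.2. Without regained responses, the upward direction follows from the definitions. The size does not. At a median of 130 days the 30-day estimate is about 5.5 to 7 points too high and the median about 12 to 15 days too long; at 166 days the 30-day excess is about 4.5 to 6 points. With half of the early losses regained it is about 3 points at 130 days. These figures rest on exponential loss, assumed response timing and Phase 1 medians from a mixed population, with no source specific to this trial. SAP 7.3.2 plans no between-arm test of DOR, and SAP 3.2 gives secondary endpoints no multiplicity adjustment. The Day 28 response and Month 6 nonrelapse mortality tests are unaffected. It should still be corrected, because a stated rule gives a biased estimate and the remedy is cheap.

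**What to change.** In SAP 7.3.2:

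1. For Day 28 responders, start the clock at Day 28 and keep that section's event definition (progression or death). Alternatively, keep the first-response clock with delayed entry at Day 28, so that earlier time does not count as time at risk. The Day 28 origin is simpler: under delayed entry, the first weeks of the curve rest only on those who responded late.
2. Specify the same Kaplan-Meier output (curves, medians, 1- to 24-month estimates) for all responders in the full analysis set, timed from first response, as Protocol 9.4.2 defines the endpoint.

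The cost is SAP wording and one set of tables, with no new data. Reported DOR becomes slightly less favourable.

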7.3.3. Alternative Ways of Calculating Duration of Response for Day 28 Responders

There are 2 other ways of calculating DOR for Day 28 responders:

- **DOR alternate approach 1** – DOR is defined as the interval from Day 28 to either death or initiation of new anti-GVHD therapy, including a higher corticosteroid dose than that administered at Day 1, whichever is earlier.
- **DOR alternate approach 2** – DOR is defined as the interval from Day 28 to the earliest of death, worsening from best response at or after Day 28 in any organ stage, or initiation of new anti-GVHD therapy (including a higher corticosteroid dose than that administered at Day 1).

Summary statistics and KM estimate will be provided by treatment group. Kaplan-Meier plots will also be provided.

7.3.4. Subgroup Analyses for Primary Endpoint

The primary endpoint will be tabulated and forest plots for odds ratios will be generated for the following subgroups:

- Age group (18-65 vs > 65 years)
- MacMillan ([2015](#)) age group: (18-40 years vs >40 years)
- Sex
- Race (White vs non-White)

- Region (North America vs Western Europe vs Rest of world)
 - **North America:** Canada, United States
 - **Western Europe:** Belgium, Denmark, France, Germany, Italy, Netherlands, Spain, Sweden, Switzerland, United Kingdom, Austria, Finland, Greece, Portugal, Switzerland, Ireland
 - **Rest of world:** Australia, Chile, Israel, Japan, South Korea, Mexico, New Zealand, Poland, Russia, South Africa, Czech Republic, Hungary, Singapore, Taiwan
- HLA/donor source category (Identical, Matched related, Matched unrelated, Mismatched related, Mismatched unrelated, Other, Missing)
- Type of Allogeneic Transplant (Bone Marrow, Peripheral Blood Stem Cell, Cord Blood, Other)
- Baseline aGVHD grade
- Skin involvement at Baseline (Yes or No)
- Lower GI involvement at Baseline (Yes or No)
- Upper GI involvement at Baseline (Yes or No)
- Liver involvement at Baseline (Yes or No)
- Baseline GVHD risk status
- Underlying hematologic disease (malignant or non-malignant)
- Days from allo-HSCT to Day 1 (< 28 days and ≥ 28 days)
- Subjects aGVHD status determined after randomization (had aGVHD, did not have aGVHD)

7.4. Analysis of the Secondary Efficacy Endpoints

7.4.1. Key Secondary Endpoint Analysis

Nonrelapse mortality is defined as death due to causes other than malignancy relapse. For the primary analysis, the NRM rate will be estimated using the proportion of subjects with a death due to causes other than malignancy relapse within the subjects who were known alive at Day 180 or who had such a death. Reasons for not including a subject in this proportion include:

- Subject was alive and had not reached Day 180
- Death due to malignancy relapse
- Subject ended study participation prior to Day 180 (summarized by reason for study withdrawal)

A sensitivity analysis will also be conducted estimating the NRM rate using the KM estimator for each treatment.

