Table 2: Operation Characteristics Using Hwang-Shih-DeCani Alpha Spending Function With Shape Parameter -4

		No. of Subjects (%)	Alpha Spent /Cumulative	Efficacy Boundary or Critical Value (as Compared With Observed Normalized Test Statistic z)	Nominal Significance /Alpha Level: $1 - \Phi(d)$	Efficacy Boundary or Critical Value at Chi-Square Test Statistic With Degree of Freedom 1
ORR at Day 28	Interim Analysis 1	112 (25.7)	–	–	–	–
	Interim Analysis 2	360 (82.6)	0.0122/0.0122	2.249810	0.0122305	5.061645
	Final	436 (100)	0.0128/0.025	2.015483	0.02192703	4.062172

If, at Interim Analysis 2, the observed number of subjects who have completed Day 28 is different from 360, then the boundaries for efficacy in [Table 2](#) will be recalculated using observed information fraction.

The interim analyses will be performed by an independent statistician and programmer not involved with the conduct of the study as described in the DMC charter.

At the Interim Analysis 2 clinical data cutoff date, the date when the 240th eligible subject randomized in the study has reached Day 180, 360 subjects are expected to have been randomized. Testing of Day 28 ORR will be conducted for subjects who have completed the Day 28 visit or withdrew from the study by the clinical data cutoff date. This means that subjects who were ongoing but had not yet reached the Day 28 visit by the Interim Analysis 2 clinical data cutoff date will be excluded from both the Day 28 ORR and NRM efficacy analyses.

[Figure 4](#) depicts the recommended decision process at Interim Analysis 2: first, testing Day 28 ORR using stratified CMH and assuming 360 subjects have completed Day 28 or withdrew from the study by the cutoff date, if observed normalized test statistic is ≤ 1.46 , it is recommended to stop the study for futility; if the observed normalized test statistic of Day 28 ORR is ≥ 2.25 , then the NRM rate at Day 180 will be tested using the Bonferroni method. If both the primary efficacy analysis and the key secondary efficacy analysis pass their corresponding efficacy boundary, the superiority of itacitinib over placebo for both the Day 28 ORR and Day 180 NRM endpoints can be claimed at Interim Analysis 2.

Table 3: Schedule of Assessments

Visit Day Item	Screening -28 to -1	Treatment ^a												EOT ^d	Retreatment ^e	Follow-Up		
		D1	D7	D14	D21	D28	D35	D42	D49	D56 ^b	D100	D180	D365 ^c			Safety ^f	GVHD ^g	Survival ^h
Informed consent	X																	
I/E criteria	X	X																

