5.3.2.1. Interim 2 Efficacy Analysis Set

The Interim 2 efficacy analysis set contains all subjects who have been randomized as of the Interim Analysis 2 clinical data cutoff date but excludes subjects who are ongoing at the clinical data cutoff date and have not finished the Day 28 visit. The Interim 2 efficacy analysis set will be used for all planned efficacy analyses at Interim Analysis 2.

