7.4.1.1. Primary Analysis of Nonrelapse Mortality Rate at Month 6 (Day 180)

For the primary analysis, NRM will be analyzed using a stratified CMH test. Month 6 NRM will be summarized using descriptive statistics by treatment group with 2-sided exact binomial 95% CIs. P-value, mean proportion difference, odds ratio, and 95% Wald confidence limits calculated from stratified CMH test will also be presented.

Let $\hat{p}_{pbo,i}$ be the estimated proportion of evaluable subjects in the placebo group in stratum i who died due to causes other than malignancy relapse prior to or on Day 180 (ie, excluding those subjects who are either ongoing and have not reached Day 180, who withdrew from study prior to Day 180, or who died due to relapse) with corresponding variance estimator $\hat{V}(\hat{p}_{pbo,i})$. Let $\hat{p}_{trt,i}$ and $\hat{V}(\hat{p}_{trt,i})$ be the same for the itacitinib group in stratum i .

The overall estimate of treatment difference in Day 180 NRM between placebo and itacitinib is defined as the following:

$$w * [\hat{p}_{pbo,standard} - \hat{p}_{trt,standard}] + (1 - w) * [\hat{p}_{pbo,high} - \hat{p}_{trt,high}]$$

Its 95% CI is the above estimate of difference

$$\pm 1.96 * \text{sqrt} (w^2 * (\hat{V}(\hat{p}_{pbo,standard}) + \hat{V}(\hat{p}_{trt,standard})) + (1 - w)^2 * (\hat{V}(\hat{p}_{pbo,high}) + \hat{V}(\hat{p}_{trt,high})))$$

With weight w defined by inverse of variance in 2 baseline GVHD risk groups. That is:

$$w = \frac{1/[\hat{V}(\hat{p}_{pbo,standard}) + \hat{V}(\hat{p}_{trt,standard})]}{1/[\hat{V}(\hat{p}_{pbo,standard}) + \hat{V}(\hat{p}_{trt,standard})] + 1/[\hat{V}(\hat{p}_{pbo,high}) + \hat{V}(\hat{p}_{trt,high})]}$$

7.4.1.2. Sensitivity Analysis of Nonrelapse Mortality Rate at Month 6 (Day 180) Using Kaplan-Meier Approach

A sensitivity analysis will also be conducted where NRM at Day 180 will be estimated by 1 minus the survival probability at Day 180 using the KM estimator.

A stratified test statistic for NRM rate at Day 180 is proposed as:

$$TS_{Day180NRM} = \frac{\left[\sum_{j=1}^2 (\widehat{CDF}_{pbo,j}(t=D180) - \widehat{CDF}_{trt,j}(t=D180)) \right]^2}{\sum_{j=1}^2 Var(\widehat{CDF}_{pbo,j}(t=D180) - \widehat{CDF}_{trt,j}(t=D180))}$$

$$= \frac{\left[\sum_{j=1}^2 (\widehat{CDF}_{pbo,j}(t = D180) - \widehat{CDF}_{trt,j}(t = D180)) \right]^2}{\sum_{j=1}^2 (SE(\widehat{CDF}_{pbo,j}(t = D180))^2 + SE(\widehat{CDF}_{trt,j}(t = D180))^2)}$$

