[Table 2](#) lists efficacy boundary when information fraction (ie, the percentage of subjects) is 0.826 (360 subjects complete Day 28 or withdraw from the study) at Interim Analysis 2. If the test on ORR at Day 28 crosses the boundary, then the key secondary endpoint, 6-month NRM rate, will be tested using a separate boundary using the Bonferroni method for alpha-spending (ie, 0.0125 as compared with 1-sided p-value at both interim and final analyses). Note that [Table 2](#) will be re-derived when the observed information for ORR at Day 28 is not 0.826.

Therefore, efficacy analysis at Interim 2, assuming information fraction being 0.826 (ie, 360/436) will be conducted as follows:

- E1: Obtain CMH test statistic on ORR at Day 28 (chi-square test with degree of freedom 1),
- E2: CMH test statistic will be compared with the critical value in Column 7 of [Table 2](#) (Interim 2 chi-square test critical value),
- E3: If positive on ORR at Day 28, NRM rate at Day 180 will be tested using the Bonferroni method,
- E4: If neither efficacy nor futility on Day 28 ORR is crossed, study will continue.

Assuming that at the Interim Analysis 2 data cutoff date (Day 180 of the 240th randomized eligible subject) there are approximately 360 subjects based on estimation who have been randomized, then testing of Day 28 ORR will be conducted for subjects who have completed Day 28 or withdrawn from the study upon the cutoff date. This means that, by the Interim Analysis 2 data cutoff date, subjects who were ongoing but had not reached the Day 28 visit will be excluded for both the Day 28 ORR and Day 180 NRM analyses.

Analysis of NRM rate at Day 180 will use the same method as described in Section [7.4.1](#) for final analysis but using the Interim Analysis 2 cutoff data instead. The decision process is described in [Figure 4](#).

At the Interim Analysis 2 data cutoff date, if the total number of randomized subjects in the Interim 2 analysis set is different from the predicted number 360, the efficacy boundaries will be recalculated based on the actual observed information fraction at Interim Analysis 2.

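### At Interim 2 the Month 6 NRM proportion counts non-relapse deaths among subjects with under 180 days of follow-up but drops their living peers, so the reported arm rates and exact intervals run high, although the CMH decision is essentially unaffected

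*SAP*

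**What the plan says.** SAP 7.4.1 takes non-relapse deaths as the numerator and forms the proportion "within the subjects who were known alive at Day 180 or who had such a death". Among its reasons for leaving a subject out is "Subject was alive and had not reached Day 180". SAP 7.4.1.1 repeats the rule in the estimator: a subject counts as an event if he "died due to causes other than malignancy relapse prior to or on Day 180", and ongoing subjects short of Day 180 are removed. Arm rates get exact binomial 95% intervals. The absolute difference is a weighted sum over strata ("With weight w defined by inverse of variance in 2 baseline GVHD risk groups").

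For Interim 2, SAP 9.1.2 uses the same NRM method "but using the Interim Analysis 2 cutoff data instead". The Interim 2 efficacy set in SAP 5.3.2.1 serves all efficacy analyses at that look, and it "excludes subjects who are ongoing at the clinical data cutoff date and have not finished the Day 28 visit". SAP 3.4.2 says of those same subjects that they "will be excluded from both the Day 28 ORR and NRM efficacy analyses", and SAP 9.1.2 that they "will be excluded for both the Day 28 ORR and Day 180 NRM analyses".

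The number 240 sets the cutoff (SAP 5.3.2, 3.4.2), the timing of the ORR boundary and a power statement (SAP 3.4.2). No section limits the NRM analysis set to those 240. SAP 3.4.2 allows NRM superiority to be claimed at this look.

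**The concern.** At the cutoff, a subject randomised 60 days earlier counts in full if he has died of a non-relapse cause and disappears if he is alive. Whether he is in the denominator depends on his outcome, so subjects with partial follow-up can only push the proportion up.

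What is at stake is the reporting. If both the ORR and NRM boundaries are crossed at Interim 2, the study may stop (SAP 3.4), and SAP 6 then puts the interim efficacy set in place of the full analysis set. The arm rates, their exact intervals and the absolute difference labelled as the primary NRM result would then come from this proportion.

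**Working it through.** **Inputs.**
- Day 180 NRM of 33% vs 19.8%; stratum rates of 22%/44% (control) and 12.4%/28.2% (itacitinib), strata 50:50 (SAP 3.3). The itacitinib strata average 20.3%, not 19.8%. Arm rates below use 19.8% unless stated; the weighted difference and the CMH figures use the stratum rates.
- 240 subjects with full 180-day potential follow-up and about 360 in the set (SAP 3.4.2), so 120 full and 60 partial per arm.
- One-sided NRM level 0.0125 (SAP 3.4.2).
- Assumed, because the documents do not give them: constant hazard, partial follow-up uniform over Days 28 to 180, no relapse deaths or withdrawals.

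**The plan's own figures.** Protocol 9.2 states 83% power for NRM at 207 per arm. A two-stratum CMH normal approximation gives 82.2% with continuity correction and 85.1% without, so the inputs are read correctly. SAP 3.4.2 states about 0.608 at Interim 2. Simulated CMH power at 0.0125 is about 0.61 with the 7.4.1 rule on 360 subjects and about 0.52 on the 240 alone.

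**Step 1: chance that a partial-follow-up subject has died.** With λ = −ln(1 − F)/180, the mean of F over Days 28 to 180 is 1 − (e^(−28λ) − e^(−180λ))/(152λ).
- Placebo: λ = 0.002225, mean 0.203.
- Itacitinib: λ = 0.001226, mean 0.118.

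**Step 2: expected proportion** = deaths / (deaths + known alive at Day 180).
- Placebo: deaths 120 × 0.33 + 60 × 0.203 = 51.8; alive 120 × 0.67 = 80.4; 51.8/132.2 = 39.2%.
- Itacitinib: deaths 120 × 0.198 + 60 × 0.118 = 30.9; alive 120 × 0.802 = 96.2; 30.9/127.1 = 24.3%. Built from the stratum rates it is 24.9%, against a true 20.3%.

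**Step 3: odds ratio.** (30.9/96.2)/(51.8/80.4) = 0.498, against a true 0.501. Deaths rise by nearly the same factor in both arms (51.8/39.6 = 1.31; 30.9/23.8 = 1.30), so the ratio hardly moves. Simulated CMH type I error at nominal 0.0125 is about 0.011.

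**Step 4: weighted difference of SAP 7.4.1.1**, 60 full and 30 partial per arm and stratum.

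| Stratum | Placebo | Itacitinib | Difference | Variance |
|---|---|---|---|---|
| Standard | 26.8% | 15.5% | 11.3 | 0.00517 |
| High | 50.8% | 33.9% | 17.0 | 0.00710 |

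The standard-risk weight is (1/0.00517)/(1/0.00517 + 1/0.00710) = 0.578, and the difference is 0.578 × 11.3 + 0.422 × 17.0 = 13.7 points, SE 5.5. With unbiased rates the weight is 0.616 and the difference is 0.616 × 9.6 + 0.384 × 15.8 = 12.0. The shift is 1.7/5.5, about 0.3 SE.

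**Step 5: interval coverage.** Simulated coverage of the true Day 180 rate by the exact 95% interval is about 72% (placebo) and 79% (itacitinib).

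**Step 6: range at 360 subjects.** Partial follow-up weighted to recent entry gives 37.9% vs 23.3%; weighted to older entry, 40.4% vs 25.3%. Front-loaded deaths (Weibull shape 0.7) give 40.0% vs 24.9%. The bias grows with the number of partial subjects: 41.4% vs 26.0% if the set held 410.

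**Step 7: Kaplan-Meier on the same 360 subjects**, stratum rates: about 33% and 20%, with a weighted difference of 12.1 points and SE about 4.7.

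**The case against.** The 240 subjects appear three times in SAP 3.4.2, so one could read the NRM analysis as meant for them. But each mention concerns the cutoff, the ORR boundary or power. If NRM were confined to subjects with 180 days behind them, there would be no need to exclude those short of Day 28 from it.

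The test is sound, and Kaplan-Meier (SAP 7.4.1.2) and cumulative incidence (SAP 7.4.3) estimates are already planned. If NRM does not cross, the study continues to a final analysis without this bias. All of that stands and limits the point to what is reported at Interim 2. It does not remove it, because the primary label stays on the biased number.

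Kaplan-Meier is not a clean cure either. It censors relapse deaths (SAP 7.4.1.2), so with an assumed 5% to 15% relapse deaths by Day 180 and constant hazards, a true 33% becomes 34.0% to 36.2%. This stands, and it is why cumulative incidence is the better lead estimate.

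SAP 10.2.1 says that both the definition and the analysis of Month 6 NRM were refined after Health Authority feedback. The feedback is not in the documents, so moving the lead estimate off the proportion could touch it. That also stands.

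**Conclusion.** The concern holds as a matter of estimation at Interim 2. At the projected 360 subjects and under the stated assumptions, the arm rates run about 6 points (placebo) and 4.5 points (itacitinib) high, their exact intervals under-cover, and the weighted difference is inflated by about 1.7 points if the planned effect is real. The size depends on accrual and death timing, which the documents do not give. The direction does not.

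Four stronger readings are tempting, and the documents do not support them.
- That the NRM claim or its type I error is compromised: the odds ratio and the CMH rejection rate are essentially unchanged, and with no effect both arms shift alike.
- That the final analysis shares this bias: by then every subject has reached Day 180 or left. A separate upward shift, from dropping relapse deaths and withdrawals, is present at both looks. With an assumed 10% relapse deaths, a true 33% becomes 0.33/0.90 = 36.7%, so comparability with the 33% planning rate is not fully restored at the final analysis either.
- That the set will hold 410 to 435 subjects because SAP Appendix D lists those sizes: they are boundary look-up values, and the projection is 360.
- That the closeness of 0.608 to 0.61 shows which set the plan's simulation used: its assumptions are not given.

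**What to change.** Keep the CMH test. In SAP 7.4.1 and 9.1.2, state that at Interim 2 the lead Day 180 NRM rates and intervals come from the type II cumulative incidence of SAP 7.4.3, with relapse death as the competing event. Add a stratum-weighted difference and interval, built from the Day 180 estimates and standard errors in the form that SAP 7.4.1.2 already gives for Kaplan-Meier. The Kaplan-Meier estimates are an acceptable substitute if the SAP says that they censor relapse deaths and so run slightly high. Keep the proportion as a supplementary output, and state that the p-value and the estimate come from different subject sets. No change is needed at the final analysis for this reason.

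The cost is SAP wording, one added formula, and confirmation that the change fits the Health Authority feedback. The cutoff (17 APR 2019) preceded SAP Amendment 1 (23 JUL 2019), and the documents do not show whether Interim 2 results had been seen. SAP 9.1.2 keeps the sponsor blinded, while Protocol 4.2 lets an unblinded sponsor statistician pass on aggregated data by treatment cohort. The change should therefore be dated and documented, with a record of who had seen unblinded Interim 2 data.

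Restricting the proportion and the test to subjects randomised at least 180 days before the cutoff, whatever their outcome, also removes this bias. It lowers Interim 2 power from about 0.61 to about 0.52, so it is a trade-off and not the preferred fix.
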